**Table 8–2: Derivation of time to first seizure**

Missing date of first seizure but seizures recorded				No evidence of seizures on the study			
V2	V3	V4	Date used	V2	V3	V4	Date used
M	M	>0	E-V1/1BRV [a]	M	M	M	C-V1
M	>0	NA	E-V1/1BRV [a]	0	M	M	C-V2
>0	NA	NA	E-V1/1BRV	M	0	M	C-V1
0	>0	NA	E-V2	M	M	0	C-V1
0	0	>0	E-V3	0	0	M	C-V3
M	-	>0	E-V1/1BRV [a]	0	M	0	C-V2
0	-	>0	E-V2	M	0	0	C-V1
-	>0	NA	E-V1/1BRV [a]	0	0	0	C-V4
-	M	>0	E-V1/1BRV [a]	0	Disc BRV	NA	C- Last BRV
				M	Disc BRV	NA	C-V1

[a] The rationale behind using V1/1BRV in this scenario is based on it being unknown when exactly between V1 and V4 that the first seizure event occurred. V1/1BRV is more conservative and hence will be used, however a sensitivity analysis may be performed if there are a lot of patients with missing data.

Note: M=patient is missing seizure data at this visit but attended the visit, - = patient missed entire visit, NA=Visit is not applicable/not required to be considered in this scenario, V=Visit, C=Censor, E=Event, 1BRV= Date of first dose of BRV, Last BRV= date of last dose of BRV.

Note: V1/1BRV implies the date of the first dose of BRV should be used if it is later than V1 to avoid negative time to events and under-reporting of potential seizure events. For patients with no evidence of seizures on the study, negative censoring times are acceptable as it is equivalent to censoring the patient on Day 1.

The time to first seizure from the date of first dose of BRV will be analyzed using Kaplan-Meier methods, from which the median time to first seizure (and 95% CI) will be calculated, along with 25% and 75% quartiles (and 95% CI for the quartiles). In addition, the cumulative number of events, number at risk, and survival estimate at monthly intervals will be provided. The Kaplan-Meier plot and raw statistical procedure output will be produced for the Kaplan-Meier analysis. This will be performed on the FAS and the modified FAS.

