## **11 ASSESSMENT OF EFFECTIVENESS AND HEALTH-RELATED QUALITY OF LIFE VARIABLES**

Retention will be based on the number of patients remaining in the study and on BRV treatment at each study visit.

The treating physician will evaluate at each visit, as part of standard practice with the patient, the frequency and type of seizures experienced by the patient since the previous study visit. Seizure information will be based on the patient diary. Both paper and electronic diaries are acceptable forms. The date and the number (where possible) of epileptic seizures will be recorded on the diary and, if available, undesirable events with start and end dates, and changes in concomitant

medication. The treating physician will review the diary at each study visit and will interview the patient to obtain or clarify any missing or incomplete information.

The QOLIE-31-P Version 2 will be used to evaluate the health-related quality of life (QoL) of study patients (Cramer and Van Hammée, 2003). The QOLIE-31-P is an adaptation of the original QOLIE-31 instrument (Cramer et al, 1998) that includes 30 items grouped into 7 multi-item subscales (seizure worry [5 items], overall QoL [2 items], emotional well-being [5 items], energy/fatigue [4 items], cognitive functioning [6 items], medication effects [3 items], and social function [5 items]) and a single health status item. The subscale scores, the total score, and the health status item score are calculated according to the scoring algorithm defined in the scoring manual, with scores ranging from 0 to 100 and higher scores indicating better function. In addition to these 31 items, the QOLIE-31-P contains 7 items assessing the degree of “distress” associated with the topic of each sub-scale (ie, distress items) and 1 item asking about the relative importance of each subscale topic (ie, prioritization item).

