### 12.2.2 Analysis of secondary variables

Retention at 3 and 6 months will be summarized using the methodology described for the primary variable.

For seizure frequency variables, Baseline seizure frequency will be based on the previous 3 months to estimate the frequency per 28 days.

The following variables will be summarized using descriptive statistics:

- Absolute and percent reduction in POS frequency (seizures per 28 days) from Visit 1 (Baseline) to Visit 2 (Month 3), Visit 3 (Month 6), Visit 4 (Month 12), and Visit 4 (Month 12 and end of Observation Period)

The following variables will be summarized using number and percentage:

- Responders, defined as a patient experiencing a  $\geq 50\%$  reduction in POS frequency (seizures per 28 days), from Visit 1 (Baseline) to Visit 2 (Month 3), Visit 3 (Month 6), Visit 4 (Month 12), and Visit 4 (Month 12 and end of Observation Period)
- Seizure-free status at Visit 2 (Month 3), Visit 3 (Month 6), Visit 4 (Month 12), and Visit 4 (Month 12 and end of Observation Period)

The time to first seizure from the date of first dose of BRV will be analyzed using Kaplan-Meier methods, from which the median time to first seizure will be calculated, along with 25% and 75% quartiles.

These analyses will be performed on the FAS and may be repeated on the modified FAS.

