### 8.2.3 Time to first seizure

The time to the first seizure (days) will be calculated as:

Date of first seizure in the trial – date of first BRV administration + 1

If the exact date of first seizure cannot be determined but the patient has had seizures recorded post Visit 1, then the patient will still be counted as having an event using a conservative approach as shown in [Table 8–2](#).

For patients with no evidence of seizures, the following sequential approach will be taken which is further detailed in [Table 8–2](#):

1. For patients attending a visit but with missing seizure data, they will be censored at the date of the last visit prior to the visit with the missing seizure information.
2. For patients discontinuing BRV study medication before experiencing their first seizure, they will be censored at the date of last administration of BRV while in the study.
3. For patients with no recorded seizures and still on BRV study medication, they will be censored at the date of last visit.

As the approach used is very conservative, if there are a lot of patients censored in the early visits due to missing data or with early events due to missing data, a sensitivity analysis may be performed.

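### SAP Table 8-2 dates undated first seizures at the start of their visit interval and treats those dates as exact, so time to first seizure is estimated too short by an amount set by an undated share that the documents do not give

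*SAP*

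**What the plan says.** Time to first seizure is a secondary variable. Protocol 12.2.2 specifies Kaplan-Meier, "from which the median time to first seizure will be calculated, along with 25% and 75% quartiles". SAP 8.2.3 computes the time as "Date of first seizure in the trial – date of first BRV administration + 1", so an event on the date of first dose has time 1.

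For undated first seizures, SAP 8.2.3 begins "If the exact date of first seizure cannot be determined but the patient has had seizures recorded post Visit 1" and continues "then the patient will still be counted as having an event using a conservative approach as shown in" Table 8-2. The table dates the event as follows:
- seizures reported at Visit 2: the row reads ">0 NA NA E-V1/1BRV";
- zero at Visit 2, seizures at Visit 3: the Visit 2 date;
- zero at Visits 2 and 3, seizures at Visit 4: the Visit 3 date;
- Visit 2 missed or without seizure data: back to Visit 1 or first BRV, even when seizures are first reported at Visit 4;
- zero at Visit 2, Visit 3 missed, seizures at Visit 4: the Visit 2 date.

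A table note makes V1/1BRV the later of Visit 1 and first dose. That is Day 1 unless Visit 1 falls after the first dose.

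There are two mentions of a sensitivity analysis, both optional. SAP 8.2.3 calls the approach very conservative and allows one if many patients are affected. Footnote [a] of Table 8-2 allows one for the rows with a missed visit or missing seizure data: "V1/1BRV is more conservative and hence will be used, however a sensitivity analysis may be performed". The Visit 2 row above does not carry that footnote. For patients without evidence of seizures, a further note says "negative censoring times are acceptable as it is equivalent to censoring the patient on Day 1".

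**The concern.** A patient known only to have had a first seizure between two visits is interval-censored. Table 8-2 replaces the interval by its left end and passes that date to Kaplan-Meier as if observed. Calling this conservative would be a defence if the error protected a comparison. Here there is one treatment group (SAP 3.6) and no inferential analysis (SAP 3.1). The output is an estimate: median, quartiles, confidence intervals and monthly survival. An error in a known direction is simply bias, and the confidence intervals do not reflect it. Nothing in the plan obliges anyone to measure it, or to count how many event dates were imputed.

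**Working it through.** **The plan's own figure.** The documents give no figure for time to first seizure. Their only design figure is for retention: 1.96² × 0.25 / 0.05² = 384.2, so 385, with half-width 1.96 × √(0.25/385) = 0.0499. Also 385/0.9 = 428 against 430 planned initially. Both reproduce, and 385 is used as the sample size below.

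**Inputs from the documents.** The +1 formula and Table 8-2; visits at Days 90 and 180 (Table 8-1 footnote); last visit at a nominal Day 360 (SAP 8.1.1 mentions a 360-day target; Table 8-1 uses Day 330).

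**Assumptions, not in the documents.** Undated share u of 5% to 50%, at random; exponential time to first seizure with true median m of 7 to 200 days; all visits attended, no dropout. One alternative uses lognormal seizure rates with a median of 2 per 28 days.

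**Direction.** Every imputed date is at or before the true date, so with follow-up complete over the interval the curve is lower or equal everywhere and no quantile can lengthen. One qualification: if patients are censored inside the interval, an event moved earlier meets a larger risk set, and the curve beyond the true date can end slightly higher.

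**Closed form.** F(90) = 1 − 2^(−90/m). Under Table 8-2 about u × F(90) of patients become Day 1 events, so the 25% quartile is Day 1 once u × F(90) ≥ 0.25 (genuine Day 1 seizures lower the threshold slightly):
- m = 30: F(90) = 0.875; u = 0.25/0.875 = 29%
- m = 60: F(90) = 0.646; u = 0.25/0.646 = 39%
- m = 120: F(90) = 0.405; u = 0.25/0.405 = 62%
- m = 200: F(90) = 0.268; u = 0.25/0.268 = 93%

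Before Day 90 the quantile q solves u × F(90) + (1 − u) × F(t) = q. For m = 60 and u = 0.30 the Day 1 mass is 0.30 × 0.646 = 0.194.
- Median: F(t) = (0.5 − 0.194)/0.7 = 0.437, so t is about 50 days instead of 60.
- 25% quartile: F(t) = (0.25 − 0.194)/0.7 = 0.080, so t is about 7 days instead of 25.

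**Simulation** (385 patients, 40 replicates; 25% quartile/median/75% quartile in days):

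| True median | Undated | True dates | Table 8-2 | Interval-censored |
|---|---|---|---|---|
| 30 | 10% | 14/31/62 | 10/27/59 | 14/31/62 |
| 30 | 30% | 13/31/61 | 1/19/54 | 13/31/62 |
| 60 | 10% | 25/61/122 | 21/58/119 | 25/61/122 |
| 60 | 30% | 26/61/120 | 7/50/105 | 25/61/121 |
| 60 | 40% | 25/61/122 | 1/46/94 | 25/61/123 |
| 120 | 30% | 51/121/243 | 37/101/211 | 50/120/242 |

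Across all exponential scenarios at 5-10% undated, the 25% quartile moves 0 to 5 days and the median 0 to 8 days, except up to 14 days when the true median is 200. The chance that the 25% quartile is Day 1 is 90% at 30% undated with m = 30, 76% at 40% with m = 60, and about nil up to 40% with m = 120. With lognormal rates the true values are 3/9/28; Table 8-2 gives 2/8/26 at 10% undated and 1/6/23 at 20%.

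**Negative censoring times.** Footnote a of Protocol Table 17-1 allows the first dose on a day other than Visit 1. If Visit 1 is the day before, censoring at Visit 1 gives −1 + 1 = 0. That patient is outside the Day 1 risk set, where the imputed events sit; a patient censored on Day 1 is inside it. The two are not equivalent. As an illustration, 48 Day 1 events among 477 patients (530 × 0.9) give 48/477 = 10.1%. Removing 10 such patients gives 48/467 = 10.3%.

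**Table 8-1 against Table 8-2.** For an undated first seizure, Table 8-1 uses the visit before the earliest visit with seizures. Where seizure data are missing at Visits 2 and 3 and seizures are recorded at Visit 4, that is the Visit 3 date. Table 8-2 gives Visit 1 or first BRV. One patient can carry two first-seizure dates.

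**The case against.** The undated share drives everything, it is not in the documents, and they suggest that dates will mostly be captured. Diary use is an entry criterion (Protocol 8.1), seizure date is a scheduled item at every visit (Protocol Table 17-1), and the physician interviews the patient to fill gaps. The diary sentence, "The date and the number (where possible) of epileptic seizures will be recorded on the diary", is weak evidence of missing dates, since its qualifier follows the number rather than the date. At low shares the shift is a few days. The SAP discloses the conservatism, the by-patient listing shows first-seizure dates, the bias runs against the product, and the primary retention result is untouched. The protocol also specifies Kaplan-Meier.

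Most of this stands, and it limits the point. A reader might infer that the reported quantiles would reflect diary completeness rather than seizure timing, or that the lower quartile will be Day 1. The documents support neither, because both need a high undated share that nothing in them establishes. If undated seizures come mainly from patients with frequent seizures, the true dates are early and the error is again only days. A reader might also take footnote [a] as covering every undated seizure; it does not reach the Visit 2 row behind the Day 1 result.

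What the objection does not answer is that the SAP provides nine table rows for undated first seizures, fixes the direction of error, and leaves its measurement to an undefined judgement.

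**Conclusion.** The point holds in conditional form. Table 8-2 biases the median, quartiles and early monthly estimates towards short times, strictly so where follow-up over the interval is complete. Under exponential times with dates missing at random, the bias is mostly a few days at 5-10% undated and material at around 30%: a median of 50 against 61 days when the true median is 60. A Day 1 lower quartile needs about 29% undated at a true median of 30 days and 39% at 60 days. An optional analysis with no trigger is not an adequate safeguard. The point affects one descriptive secondary variable and should be fixed. It does not follow that Kaplan-Meier must be dropped. The negative-censoring note is incorrect, but its effect is minor.

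**What to change.** Keep the Kaplan-Meier analysis required by the protocol and amend SAP 8.2.3 as follows.
- Replace the optional sensitivity analysis with a mandatory interval-censored (Turnbull) estimate on the FAS. Use exact dates where known; the interval (last visit with zero seizures or first BRV, reporting visit] for undated first seizures; and right-censoring otherwise. Report its median and quartiles with CIs next to the Table 8-2 result.
- Report the number of events with imputed dates.
- Set any censoring time below 1 to Day 1 and delete the equivalence note.
- Reconcile the first-seizure date in Table 8-1 with Table 8-2.

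If the sponsor prefers the interval-censored estimate as the main analysis, list the change in SAP 3.9. Midpoint dating is not a substitute: with a true median of 15 days and 30% undated it gives 10/28/45 against true values of 7/16/30.

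The cost is SAP wording and one extra procedure run, a less familiar curve, and CIs that need resampling or imputation. The interval-censored estimate also assumes that a missing date is unrelated to when in the interval the seizure fell, which is a further reason to show both results.

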### 8.3 Analysis of other variables

#### 8.3.1 Patient Weighted Quality of Life in Epilepsy Inventory-form 31 (QOLIE-31-P)

The QOLIE-31-P includes 30 items grouped into 7 multi-item subscales (seizure worry [5 items], overall quality of life [2 items], emotional well-being [5 items], energy/fatigue [4 items], cognitive functioning [6 items], medication effects [3 items], and social function [5 items]) and a health status item. The QOLIE-31-P total score, subscale scores, and health status item score are calculated according to the scoring algorithm described below, with scores ranging from 0 to 100 and higher scores indicating better functioning.

##### 8.3.1.1 Derivation of QOLIE-31-P scores

Subscale scores: as a first step to calculating the subscale scores, the individual responses for the 30 subscale items are rescaled to a 0 to 100 scale with higher scores reflecting better functioning; the rescaled values for each item are defined in [Section 12.1](#). Each subscale score is then calculated by summing the rescaled responses for that subscale and dividing by the number of items with a non-missing response. A subscale score will be calculated only if at least 50% of the items within the subscale are present.

Total score: total score is calculated as a weighted sum of the subscale scores based on the weighting in [Section 12.1](#). Total score will be missing if at least 1 subscale score is missing. Total score will range from 0 to 100 with a higher score reflecting better functioning.

Health status item: responses for the health status item are a multiple of 10 ranging from 0 to 100 with a higher score corresponding to a better health status. The health status item response is analyzed without rescaling.

The change from Baseline (CFB) at each Visit for the subscale scores, total score, and health status item will be calculated as:

Derived score at post-Baseline visit – Derived score at Visit 1 (Baseline)

A clinically meaningful change (CMC) in QOLIE-31-P from Baseline is defined based on the minimally important changes in [Table 8–3](#); Borghs et al, 2012.

For each subscale and total score:

- Improvement is defined as:  $CFB \geq CMC$
- No change is defined as:  $- CMC < CFB < CMC$
- Worsening is defined as:  $CFB \leq - CMC$

Table 8-3: QOLIE-31-P Clinically Meaningful Change Criteria	
Subscale Score	Clinically Meaningful Change (CMC)
Energy/Fatigue	5.25
Emotional Well-Being	4.76
Social Functioning	3.95
Cognitive Functioning	5.34
Medication Effects	5.00
Seizure Worry	7.42
Overall Quality of Life	6.42
Total Score	5.19

### 8.3.1.2 Analysis of QOLIE-31-P scores

All QOLIE-31-P analyses will be performed on the FAS and the modified FAS.

Descriptive statistics will be presented for QOLIE-31-P: 7 multi-item subscales, the health status item, and total score, and the changes from Visit 1 (Baseline) to Visit 2 (Month 3), Visit 3 (Month 6), Visit 4 (Month 12) and Visit 4 (Month 12/Withdrawal). As described in [Section 3.2.2](#), Visit 4 (Month 12/Withdrawal) visits will be mapped to the appropriate scheduled visit and Visit 4 (Month 12) will only include patients completing the study.

The number and percentage of patients with clinically meaningful changes in QOLIE-31-P total and subscale scores from Baseline (improvement, no change, or worsening) will be presented for Visit 2 (Month 3), Visit 3 (Month 6), Visit 4 (Month 12) and Visit 4 (Month 12/Withdrawal).

A question glossary and by-patient listings of QOLIE-31-P scores (including all items of the subscale scores, the total subscale scores, the total score, the health status item, changes from Baseline, and whether patients achieved a clinically meaningful change) will be provided for the All Subjects Documented set.

### 8.3.2 EpiTrack

All EpiTrack analyses will be performed on the FAS and the modified FAS. EpiTrack score after age correction will be referred to as "EpiTrack total score".

Descriptive statistics will be provided for the EpiTrack total score calculated as described in [Section 12.2](#) and the individual point scores of the 6 subtests. Visit 4 (Month 12/Withdrawal) visits will be mapped to Visit 3 (Month 6) if they are within the windows described in [Section 3.2.2](#). EpiTrack results by visit and the changes from Visit 1 (Baseline) to Visit 3 (Month 6) and Visit 4 (Month 12) will also be displayed. The same age correction (age at Visit 1) will be applied at all visits even if a patient changes age category during the study. If any of the individual point scores are outside of the plausible range then they will be set to missing in the tables but will be listed in the listings. If a patient is missing any of the individual point scores or the individual point score is outside of the plausible range then the EpiTrack total score will be missing. Change from Baseline will be calculated as:

$$\text{Post-Baseline score} - \text{Baseline score.}$$

The number and percentage of patients in the following categories (calculated as described in [Section 12.2](#)) will be provided:

- Point score categories (rated 1-7 for Interference, Numbers, Numbers and letters, and Maze test; 2-7 for Verbal fluency and 3-7 for Inverted digit span)
- Cognitive performance categories (excellent, average, mildly impaired, or significantly impaired) at Visit 1 (Baseline), Visit 3 (Month 6), and Visit 4 (Month 12)
- Significant change categories of cognitive function (improved, unchanged, or worsened) for:
  - Visit 3 (Month 6) compared to Visit 1 (Baseline)
  - Visit 4 (Month 12) compared to the Visit 1 (Baseline)
  - Visit 4 (Month 12) compared to Visit 3 (Month 6).

By-patient listings of 6 EpiTrack individual subtest scores, the change from Baseline for the 6 individual subtest scores, and the age correction, EpiTrack total score and change from Baseline, cognitive performance categories, and significant change evaluation will be provided for the All Subjects Documented set.

### **8.3.3 Clinical Global Impression of Change (CGIC) and Patient's Global Impression of Change (PGIC)**

The CGIC describing the patients condition over the past 4 weeks compared to Baseline (as assessed by the treating physician) and the PGIC describing how the patient felt over the past 4-weeks compared to before they entered the study, will each be assessed at Visit 2 (Month 3), Visit 3 (Month 6), and Visit 4 (Month 12) according to 7 categories (1=Very much improved, 2=much improved, 3=minimally improved, 4=no change, 5=minimally worse, 6=much worse, and 7=very much worse).

For both scales (CGIC and PGIC) the above categories will be collapsed into Improvement, No change, and Worsening as follows:

- Improvement: category 1, 2, or 3
- No change: category 4
- Worsening: category 5, 6, or 7

All CGIC and PGIC analyses will be performed on the FAS and the modified FAS. The number and percentage of patients with each CGIC and PGIC rating and who had improved, had no change, or worsened at Visit 2 (Month 3), Visit 3 (Month 6), Visit 4 (Month 12) and Visit 4 (Month 12/Withdrawal) will be presented. Visit 4 (Month 12/Withdrawal) visits will be mapped as described in [Section 3.2.2](#).

A by-patient listing of CGIC and PGIC including categories of improvement or worsening will be provided on the All Subjects Documented set.

### **8.3.4 Change in drug load of AEDs**

Drug load of AEDs will be calculated at first BRV administration, Visit 4 (Month 12), and Visit 4 (Month 12/Withdrawal). Drug load of AEDs will include all concomitant AEDs and LEV (recorded separately in the CRF), in addition to BRV dosing.

Only AEDs (recorded as an AED, as LEV, or as BRV dosing) that are being taken on the date of the visit will be included in the calculations. Partial dates will be imputed as described in [Section 4.2.2](#) to ensure the inclusion of any medications which have the potential to have been taken on the date of the visit.

Drug load per AED at the visit is calculated as: daily dose (mg) / DDD, where DDD for each AED is defined in [Section 12.3](#) and daily dose for each AED is calculated as follows:

1. Convert the dose per intake into mg using the unit recorded for each AED in the CRF (ie, 1g = 1000mg)
2. Using the frequency of dose recorded, multiply the dose per intake in mg by the values shown in [Table 8-4](#).

Table 8-4: Daily dose calculation		
Frequency	Description	Multiply dose per intake by:
QD	Once daily	1
BID	Twice daily	2
TID	3 times daily	3
QID	4 times daily	4
5XD	5 times daily	5
6XD	6 times daily	6
QOD	Every other day	1/2
QAM	Every morning	1
QPM	Every evening	1
QS	Every week	1/7
Q2S	Every 2 weeks	1/14
BIS	Twice per week	2/7
TIS	3 times per week	3/7
QM	Every month	1/28
BIM	Twice per month	2/28
TIM	3 times per month	3/28
Q2M	Every 2 months	1/56
Q3M	Every 3 months	1/84
PRN	As needed	Excluded from calculation

The drug load per AED at each visit will be added together to give a total AED drug load per visit. To avoid an underestimation of the drug load on the first and last visits (on which only 1 of the usual 2 doses may have been recorded), AED drug load at first BRV administration will be

calculated for the Day 2 for all patients and the last available record with morning and evening dosage will be used for the Visit 4 drug load analysis.

All drug load analyses will be performed on the FAS and the modified FAS.

The total AED drug load at first BRV administration (Baseline), Visit 4 (Month 12), and Visit 4 (Month 12/Withdrawal), and the change from Baseline will be summarized by descriptive statistics. Change from Baseline is defined as: Total AED drug load at Visit 4 (Month 12) or Visit 4 (Month 12/Withdrawal) – total AED drug load at first BRV administration (Baseline).

The number of AEDs (including LEV, VNS use and BRV) taken per patient at first BRV administration (Baseline), Visit 4 (Month 12), and Visit 4 (Month 12/Withdrawal), and change from Baseline will be summarized by descriptive statistics. The number of AEDs at first BRV administration (Baseline) will be equal to the number of AEDs at Study Entry as described in [Section 6.4](#). Patients with VNS use at first BRV administration (Baseline) will be considered to have VNS use during the entire study and as such it will be counted as an AED at Visit 4 (Month 12) and Visit 4 (Month 12/Withdrawal) as appropriate. The total number of AEDs at a visit is a count of the number of concomitant AEDs, LEV, or BRV that are being taken on the date of the visit with partial dates imputed as described in Section 4.2.2, plus any VNS use. Change from Baseline is defined as: Total number of AEDs at Visit 4 (Month 12) or Visit 4 (Month 12/Withdrawal) – total number of AEDs at first BRV administration (Baseline).

A by-patient listing of drug load data will be provided on the All Subjects Documented set. The listing will include the total drug load, number of AEDs (including LEV and BRV) taken per patient, the changes from Baseline, AEDs taken (including LEV or BRV), the daily dose per given product, DDD, drug load per AED, and frequency at each visit.

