#### **3.2 General study level definitions**

##### **3.2.1 Relative day**

The relative day of a given date “D” will be calculated as follows:

- For days prior to the first BRV administration:  
D – date of first BRV administration
- For days on or after date of first BRV administration and prior to or on the day of last BRV administration:  
D – date of first BRV administration + 1
- For days after the last BRV administration:  
D – date of last BRV administration  
A “+” will be shown at the start to denote posttreatment days

Hence, the first day of BRV administration is Day 1, the day before the first BRV administration is Day -1, and the day after the last dose of BRV is Day +1. Relative day will not be calculated for partial dates.

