### **3.3 Definition of Baseline values**

In this NIS, Baseline is defined as the data collected at Visit 1. For prior and concomitant medications and for AED drug load, Baseline is defined as first BRV administration. For seizure frequency variables, Baseline is defined in [Section 8.2.2.1](#).

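### Baseline AED drug load is taken on Day 2 for every drug, so an AED whose end date is Day 1 drops out of the load but stays in the AED count

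*SAP*

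**What the plan says.** SAP 8.3.4 defines the content of the load: "Drug load of AEDs will include all concomitant AEDs and LEV (recorded separately in the CRF), in addition to BRV dosing". An AED enters only if it is one of those "that are being taken on the date of the visit will be included in the calculations". The Baseline load is labelled as the load at first BRV administration, but is "calculated for the Day 2 for all patients". The reason given is that only one of the two usual doses may be on record for the first and last visits.

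Three other places bear on the Baseline day:

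- SAP 3.3: "For prior and concomitant medications and for AED drug load, Baseline is defined as first BRV administration". Under SAP 3.2.1, "the first day of BRV administration is Day 1".
- SAP 8.3.4, on the count: "The number of AEDs at first BRV administration (Baseline) will be equal to the number of AEDs at Study Entry". SAP 6.4 defines study entry by what is taken on the day of first BRV, so the count is taken on Day 1.
- SAP 10.1 uses Day 2 for the starting BRV dose because some patients take only an afternoon BRV dose on Day 1.

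**The concern.** The Day 2 rule answers a problem with BRV. For an AED already in use, SAP Table 8-4 builds the daily dose from the dose per intake and the recorded frequency, so a record that covers Day 1 already yields the full daily dose. Moving these AEDs to Day 2 corrects nothing, and it can remove a drug whose last day was Day 1.

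Protocol 4.3 treats the number of products and the ratio of dose to DDD as components of one drug-load variable. Under the SAP their Baselines fall on different days. For a patient who stops another AED on the day BRV starts, the two can disagree about whether anything was withdrawn, and the load change then depends on whether the old drug ended on Day 1 or on Day 2. Such switches are plausible: SAP 6.2 lists side effects of, or intolerance to, a current AED among the reasons for starting BRV, and Protocol Table 17-1 asks for LEV dates, dosages and reason for discontinuation.

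**Working it through.** The documents state no drug-load result, so there is no figure of the plan's to reproduce. The check applies SAP 8.3.4 to one dated set of records.

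**Inputs from the SAP.** Load per AED = daily dose / DDD; total load = sum over AEDs taken on the index day; change = Visit 4 total minus Baseline total. Table 12-1 gives DDD 1500 mg for LEV and 100 mg for BRV.

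**Assumed inputs, not in the documents.** LEV 1500 mg/day with a complete end date of Day 1; one background AED held constant at 1.00 DDD; BRV 100 mg/day on Day 2 and at Visit 4, with 50 mg on record for Day 1.

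**Loads.** LEV 1500/1500 = 1.00; BRV 100/100 = 1.00 (50/100 = 0.50 on Day 1).

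| Baseline rule | LEV | Background | BRV | Baseline total | Visit 4 total | Change |
|---|---|---|---|---|---|---|
| SAP: all on Day 2 | 0 | 1.00 | 1.00 | 2.00 | 2.00 | 0.00 |
| Other AEDs on Day 1, BRV on Day 2 | 1.00 | 1.00 | 1.00 | 3.00 | 2.00 | -1.00 |
| All on Day 1 | 1.00 | 1.00 | 0.50 | 2.50 | 2.00 | -0.50 |

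**Count for the same patient.** LEV, background AED and BRV on Day 1 make 3; background AED and BRV at Visit 4 make 2; change -1. This counts BRV at Baseline, as SAP 8.3.4 says. SAP 6.4 does not state that the study-entry count includes BRV; whether it does is a separate matter, and LEV is in the Baseline count either way.

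**Effect of the end date.** If LEV ends on Day 2, or continues beyond it at the same dose, the SAP Baseline is 3.00 and the change -1.00, the same as in the second row. One day's difference in the end date moves the load change by the full load of the drug. If LEV was last taken the day before BRV, it is historical under SAP 6.4 and both rules give a change of 0.00.

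**Size per patient.** The difference between the first two rows equals the stopped drug's dose / DDD:

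| LEV mg/day (assumed) | 1000 | 1500 | 2000 | 3000 |
|---|---|---|---|---|
| Removal missed (DDD) | 0.67 | 1.00 | 1.33 | 2.00 |

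**Size in the mean.** Shift = share of affected patients x dose / DDD. The share is not in the documents. Over an assumed 5% to 30% and the LEV doses above, the shift runs from 0.05 x 0.67 = 0.03 to 0.30 x 2.00 = 0.60 DDD. This shows how the effect scales; it is not an estimate for this study.

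**The case against.** The best defence is that SAP 8.3.4 is a specific, disclosed and reasoned rule that puts the general Baseline definition of SAP 3.3 into operation. That has some force: a one-day shift from the general definition would matter little by itself. It does not answer the mismatch between load and count, and the reason given does not extend to AEDs other than BRV.

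The information is also not lost. The AED count keeps the stopped drug, and the listings in SAP 6.4 give dose and start and end dates of concomitant AEDs, with the reason for discontinuation for LEV. That stands and limits the harm.

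Three stronger readings are tempting, and the documents do not support them.

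- A reader might infer that the load change misses all the load that BRV replaced. It misses only AEDs with a complete end date of Day 1. An AED tapered or stopped on Day 2 or later is in the Baseline load at its Day 2 dose. A month-only end date is imputed to the last day of the month (SAP 4.2.2), which keeps the drug in the Day 2 load unless Day 1 is itself the last day of the month.
- A reader might measure the error against the load before BRV. The SAP's Baseline includes BRV by design, so that is a different quantity. In the example the pre-BRV load is LEV 1.00 + background 1.00 = 2.00 and the change from it is also 0.00; it would be +0.33 at LEV 1000 mg/day and -1.00 at 3000 mg/day.
- A reader might infer that overnight replacement is common here. The Protocol cites one small LEV-to-BRV switch study as background. No passage describes same-day replacement or says how often it occurs.

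**Conclusion.** The point holds in a narrow form. Under SAP 8.3.4 a non-BRV AED with a complete end date of Day 1 contributes 0 to the Baseline load, 0 to the Visit 4 load and so 0 to the change, while the Baseline AED count includes it. For that patient the load change is off by the drug's dose / DDD: 1.00 in the example, which rests on assumed doses and a constant background AED. The size in the study cannot be derived, because the number of patients with such an end date is not given.

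Severity is minor. Drug load is listed among the other variables and is only summarised descriptively; retention and the seizure outcomes do not depend on it. It is still worth correcting, because the result otherwise turns on the timing of a switch and two summaries in one section can disagree.

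**What to change.** In SAP 8.3.4:

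1. Apply the Day 2 rule to the BRV component only.
2. Take all other AEDs, including LEV, as recorded on Day 1, the study-entry definition in SAP 6.4, so that load and count share one reference day for these drugs.
3. Report Baseline, Visit 4 and change for non-BRV AED load and for BRV load separately, as well as in total.
4. Align SAP 3.3, 6.4 and 8.3.4 on the Baseline day.

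Moving everything to Day 1 is not a clean alternative, because it brings back the partial first-day BRV dose (third row of the first table). The day before first BRV would also pick up drugs last taken then, but it departs from SAP 3.3 and 6.4, and for AEDs stopped before BRV the documents show dose and date collection only for LEV.

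The cost is a change of SAP wording and a small change in the derivation; doses and dates of concomitant AEDs are already collected. One small downside remains: on Day 1 the stopped AED and BRV both count in the total. The separate lines make that visible.
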